6.2. Background Characteristics

6.2.1. Subject Disposition

The number and percentage of subjects in the following categories will be summarized by CMV serostatus (CMV-seropositive, CMV-seronegative, and overall) and vaccination group as defined in [Section 6.1](#) based on Randomized Set:

- Randomized Set
- Solicited Safety Set
- Safety Set
- Full Analysis Set

- PP Set

The percentage will be based on subjects in that vaccination group within the Randomized Set. A separate table based on the Safety Set reporting the number and percentage of subjects in the Solicited Safety Set will be provided.

The number of subjects in the following categories will be summarized based on subjects screened:

- Number of subjects screened
- Number and percentage of screen failure subjects and the reason for screen failure

The percentage of subjects who screen failed will be based on the number of subjects screened. The reason for screen failure will be based on the number of subjects who screen failed.

The number and percentage of subjects in each of the following disposition categories will be summarized by CMV serostatus and vaccination group based on the Randomized Set:

- Received each study vaccine
- Prematurely discontinued study vaccine and the reason for discontinuation
- Completed study
- Willing to enroll in Study P202-EXT
- Prematurely discontinued the study and the reason for discontinuation

The denominator for all percentages will be the number of subjects in that vaccination group within the Randomized Set.

A subject disposition listing will be provided including informed consent, subjects who completed study, subjects who were willing to enroll in Study P202-EXT, subjects who discontinued from study vaccine or who discontinued from participation in the study, with reasons for discontinuation. A separate listing will be provided for screen failure subjects with reasons for screen failure.

Study duration will be summarized since randomization, since first vaccination, since second vaccination, and since third vaccination. Study duration since randomization (first vaccination, second vaccination, third vaccination) will be calculated as the earliest date of (study completion, discontinuation from the study, data cutoff, or death) – date of randomization (date of first vaccination, second vaccination, third vaccination) + 1. If the

date of randomization (date of first vaccination, second vaccination, third vaccination) is not available, the corresponding duration will be zero. The summaries will be provided separately for the Safety Set, FAS for Antibody-Mediated Immunogenicity, and PP Set for Antibody-Mediated Immunogenicity.

A subject is considered to have completed the study if they complete the final visit per the protocol Schedule of Assessments, independent of how many doses were administered.

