5.3. Safety Set

The Safety Set consists of all randomized participants who received any study vaccination. The Safety Set will be used for analysis of safety except for the solicited ARs.

Subjects will be analyzed according to the vaccination group a subject received, rather than the vaccination group to which the subject is randomized to. Subjects who receive a vaccination/injection that is different from the vaccination/injection which the subject is randomized to will be summarized under the highest dose of vaccination group (i.e., mRNA-1647 **CCI** > mRNA-1647 **CCI** > mRNA-1647 **CCI** > Placebo).

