5.4. Full Analysis Set

Full Analysis Set (FAS) for Antibody-Mediated Immunogenicity

The FAS for antibody-mediated immunogenicity consists of all randomized participants who

- a) receive any study vaccination,
- b) have baseline (Day 1) antibody-mediated immunogenicity data available for those analyses that require baseline data, and
- c) have at least one post-vaccination antibody-mediated immunogenicity assessment for the analysis endpoint.

FAS for Cell-Mediated Immunogenicity

The FAS for cell-mediated immunogenicity (CMI) consists of all randomized participants who

- a) receive any study vaccination,
- b) have baseline (Day 1) CMI data available for those analyses that require baseline data, and
- c) have at least one post-vaccination CMI assessment for the analysis endpoint.

Participants will be included in the vaccination group to which they are randomized.

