5.5. Per-Protocol Sets

The Per-Protocol (PP) Set for Antibody-Mediated Immunogenicity

PP Set for Antibody-Mediated Immunogenicity consist of all FAS participants who

- a) comply with the vaccination schedule,
- b) comply with the timings of immunogenicity blood sampling to have post-vaccination results available for at least one assay component corresponding to the immunogenicity analysis objective (antibody-mediated immunogenicity endpoints), and
- c) have no major protocol deviations that impact immune response during the period corresponding to the immunogenicity analysis objective (antibody-mediated immunogenicity endpoints).

Subjects who were CMV seronegative at Screening and became CMV seropositive at baseline (before or on 1st dose of study vaccination) will be excluded from the PP Set for Antibody-Mediated Immunogenicity.

The PP Set for Antibody-Mediated Immunogenicity will serve as the primary population for the analysis of antibody-mediated immunogenicity data in this study. Participants will be included in the vaccination group to which they are randomized.

PP Set for CMI

PP Set for CMI consist of all FAS for Cell-Mediated participants who

- a) comply with the 3-dose vaccination schedule,
- b) comply with the timings of immunogenicity blood sampling to have post-vaccination results available for at least one assay component corresponding to the immunogenicity analysis objective (CMI endpoints), and
- c) have no major protocol deviations that impact immune response during the period corresponding to the immunogenicity analysis objective (CMI endpoints).

Subjects who were CMV seronegative at Screening and became CMV seropositive at baseline (before or on 1st dose of study vaccination) will be excluded from the PP Set for CMI.

The PP Set for CMI will serve as the primary population for the analysis of CMI data in this study. Participants will be included in the vaccination group to which they are randomized.

6. Statistical Analysis

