6.1. General Considerations

The Schedule of Assessments is provided in the protocol Table 1 for subjects completing all vaccinations, Table 6 for subjects completing the first 2 vaccinations only, and Table 7 for subjects who completing the first vaccination only.

Continuous variables will be summarized using the following descriptive summary statistics: the number of subjects (n), mean, standard deviation (SD), median, minimum (min), and maximum (max).

Categorical variables will be summarized using counts and percentages.

Baseline value, unless specified otherwise, will be defined as the most recent non-missing measurement (scheduled or unscheduled) collected before the first dose of study vaccination.

For the summary statistics of all numerical variables unless otherwise specified, the display precision will follow programming standards. Please see [Appendix A](#) for variable display standards.

When count data are presented, the percentage will be suppressed when the count is zero in order to draw attention to the non-zero counts. A row denoted “Missing” will be included in count tabulations where specified on the shells to account for dropouts and missing values. The denominator for all percentages will be the number of subjects in that vaccination group within the analysis set of interest, unless otherwise specified.

Study day relative to the first vaccination will be calculated as below:

- a) study day prior to the first vaccination will be calculated as: date of assessment/event – date of the first vaccination;
- b) study day on or after the date of the first vaccination will be calculated as: date of assessment/event – date of the first vaccination + 1;

Study day relative to the most recent vaccination will be calculated as below:

- a) study day prior to the first vaccination will be calculated as: date of assessment/event – date of the first vaccination;
- b) study day on or after the date of the first vaccination but before the second vaccination (if applicable) will be calculated as: date of assessment/event – date of the first vaccination + 1;

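### Study duration since a dose that was not given is coded as zero rather than missing, so mean follow-up after doses 2 and 3 is understated wherever those doses were missed

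*SAP*

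**What the plan says.** SAP 6.2.1 (Subject Disposition) defines the quantity: "Study duration will be summarized since randomization, since first vaccination, since second vaccination, and since third vaccination". Each duration "will be calculated as the earliest date of (study completion, discontinuation from the study, data cutoff, or death"), minus the start date, plus 1. If the start date "is not available, the corresponding duration will be zero". On populations the section adds: "The summaries will be provided separately for the Safety Set, FAS for Antibody-Mediated Immunogenicity, and PP Set for Antibody-Mediated Immunogenicity". It contains no restriction to participants who received the dose in question.

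The membership rules matter here. SAP 5.3: "The Safety Set consists of all randomized participants who received any study vaccination". For the FAS, SAP 5.4 likewise asks only that participants "receive any study vaccination", together with baseline data where needed and a post-vaccination assessment. The PP Set (SAP 5.5) is narrower, since its members must "comply with the vaccination schedule".

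Under SAP 6.1, continuous variables are reported with "the number of subjects (n), mean, standard deviation (SD), median, minimum (min), and maximum (max"). Also in SAP 6.1, for a participant who skips dose 2 but receives dose 3, the study day after dose 2 is coded as missing.

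**The concern.** A participant who never received a dose has no follow-up time since that dose. Giving that person a value of zero puts a code for no dose date into the same column as real follow-up times, and the mean, SD, n and minimum are then computed over both.

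The situation is foreseen. Protocol 4.1.3 and 7.1 keep participants in follow-up after they stop at dose 1 or dose 2, Appendix 2 gives them their own visit schedules, and 7.1 allows dose 2 to be missed and dose 3 still given. SAP 6.2.1 counts a participant as a completer whatever the number of doses. Someone who completes every scheduled visit can therefore enter the third-dose row with zero days.

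At stake is how the descriptive follow-up figures for doses 2 and 3 are read. A reader could take a low mean as poor retention after the dose when the cause is non-receipt. If non-receipt differs between vaccination groups, the groups will appear to have been followed for different lengths of time even if their recipients were not.

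**Working it through.** The documents state no mean follow-up after any dose, so there is no figure of the plan's own to reproduce.

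**Inputs**
- Dose days 1, 56 and 168 (Protocol 4.1.2).
- Last visit: Day 504 after three doses (Protocol 8.10), Day 420 after the first two only (Table 6), Day 336 after the first only (Table 7).
- Duration = end date − dose date + 1; zero if there is no dose date (SAP 6.2.1).
- Share p of the analysis set without the dose: not given, so a range is assumed.

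**Can zero be a real value?** A participant dosed and last followed on the same day has 0 + 1 = 1 day. The smallest real duration is 1, so zero can only be a placeholder. It also catches a dose that was given but whose date is missing.

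**Recipients who complete the planned schedule**
- Since dose 3: 504 − 168 + 1 = 337 days.
- Since dose 2: 504 − 56 + 1 = 449 days.

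**Effect of the zeros.** Reported mean = (1 − p) × mean among recipients. With every recipient at the scheduled value, the SD created by the zeros alone is that value × √(p(1 − p)).

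| p (assumed) | Mean since dose 3 | SD from zeros | Mean since dose 2 | SD from zeros |
|---|---|---|---|---|
| 0% | 337 | 0 | 449 | 0 |
| 5% | 320.1 | 73.4 | 426.5 | 97.9 |
| 10% | 303.3 | 101.1 | 404.1 | 134.7 |
| 20% | 269.6 | 134.8 | 359.2 | 179.6 |

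**A mixed example (assumed).** Take 100 participants: 90 with three doses, 6 with the first two only, 4 with the first only, all completing their own schedule. The 6 have 420 − 56 + 1 = 365 days since dose 2.
- Since dose 3, as written: mean 30,330/100 = 303.3, SD 101.6, minimum 0, n = 100. Recipients only: mean 30,330/90 = 337, SD 0, minimum 337, n = 90.
- Since dose 2, as written: mean 42,600/100 = 426.0, SD 89.7, minimum 0, n = 100. Recipients only: mean 42,600/96 = 443.8, SD 20.4, minimum 365, n = 96.
- The median since dose 3 is 337 either way.

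**Differential non-receipt (assumed).** With 20% lacking dose 3 in one group and 8% in another, the means are 337 × 0.80 = 269.6 and 337 × 0.92 = 310.0 days. That is a gap of 40.4 days, although recipients in both groups were followed for 337.

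**The case against.** The case for leaving it alone has several parts, and most of them stand as limits on importance.

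- **Nothing depends on the figure.** Adverse event percentages use the number of participants in the Safety Set (SAP 6.3.1), the immunogenicity models do not use duration, and the study tests no hypothesis. This stands.
- **The median is also reported.** On the planned schedule it does not move for any share in the table. If recipients' durations vary, it can shift: with 20% zeros, the overall median sits at the (0.50 − 0.20)/0.80 = 37.5th percentile of recipients. The objection largely stands.
- **Non-receipt is tabulated in the same section.** SAP 6.2.1 reports how many received each vaccination and why vaccination or participation stopped. Total person-days are unchanged by the zeros, so a reader could recover the recipients' mean as reported mean × N / number dosed. That stands only in part: those counts are planned for the Randomized Set, while the durations are reported in other sets. The mean could also be read as post-dose time per member of the whole set, but the SAP does not define it that way.
- **The size is assumed.** The documents give no share missing dose 2 or 3. If nobody missed a dose, there is no error. This stands.

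Two stronger readings are tempting and are not supported. A reader might infer that zero means dosed and lost on the same day; the added day makes that value 1. A reader might also infer that these tables are the evidence that the MAAE and SAE follow-up was achieved. Protocol 4.1.3 counts that follow-up from the last vaccination, whereas these rows count from the first, second and third. Even a corrected third-dose row would omit everyone who stopped earlier, and study completion is reported separately.

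**Conclusion.** The rule is wrong as written, and the consequence is minor. In the Safety Set and the FAS, whenever participants lack dose 2 or dose 3, the mean duration since that dose is understated by the proportion lacking it, n and SD are inflated, and the minimum becomes 0. The rule also departs from the SAP's own handling of a skipped dose 2 in section 6.1, and no reason is given.

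For dose 3 the understatement is 17, 34 or 67 days (337 less 320, 303 or 270) if 5%, 10% or 20% lack the dose. This assumes that recipients complete the planned schedule exactly, ignoring visit windows and dropout after dose 3. Durations since dose 1 are essentially unaffected, because every member of these sets received at least one vaccination. The PP Set should be little affected, because it requires schedule compliance. The problem is confined to a descriptive background table; no primary, secondary or exploratory endpoint changes.

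**What to change.** In SAP 6.2.1, replace the zero rule with this: the duration is missing when the dose was not given or its date is not known. State that durations since the second and third vaccination are summarised only in participants of the analysis set who received that dose and have a known date, and show that n beside the set total.

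The cost is one amended sentence and one line in the derivation, which can be made before the final database lock for which this SAP version was prepared. No information is lost, because receipt of each vaccination is already tabulated in the same section.

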6.2.2. Demographics

Descriptive statistics will be calculated for the following continuous demographic and baseline characteristics: age (years), weight (kg), height (cm), and body mass index (BMI) (kg/m^2). Number and percentage of subjects will be provided for categorical variables such as gender, race, ethnicity, CMV serostatus at screening, and baseline CMV serology. Positive baseline CMV serology will be defined as either nAb titer against epithelial cell infection or the nAb titer against fibroblast infection above the LLOQ at baseline. The summaries will be presented by CMV serostatus (CMV-seropositive, CMV-seronegative and overall) and vaccination group as defined in [Section 6.1](#) based on the Safety Set. If the Safety Set differs from the Randomized Set (eg, subjects randomized but not treated; subjects received wrong treatment), the analysis will also be conducted using the Randomized Set.

For screened failure subjects, age (years), gender, race, ethnicity will be presented in a listing.

In addition, subjects with any inclusion and exclusion criteria violation will also be provided in a listing.

6.2.3. Medical History

Medical history data will be coded by system organ class (SOC) and preferred term (PT) using the Medical Dictionary for Regulatory Activities (MedDRA).

The number and percentage of participants with any medical history will be summarized by SOC and PT based on the Safety Set. A participant will be counted only once for multiple events within each SOC and PT. SOC will be displayed in internationally agreed order. PT will be displayed in descending frequency in the total mRNA-1647 group, and then alphabetically within SOC.

Medical history data will be presented in a listing.

6.2.4. Prior and Concomitant Medications

Prior and concomitant medications and non-study vaccination will be coded using the World Health Organization (WHO) drug dictionary (WHODD).

The number and percentage of subjects using concomitant medications and non-study vaccination during the 7-day follow-up period (ie, on the day of vaccination and the 6 subsequent days) and during the 28-day follow-up period after each vaccination (ie, on the day of vaccination and the 27 subsequent days) will be summarized by CMV serostatus (CMV-seropositive, CMV-seronegative, and overall) and vaccination groups as defined in [Section 6.1](#) as follows:

- Any concomitant medications and non-study vaccination within 7 Days Post Vaccination
- Any concomitant medications and non-study vaccination within 28 Days Post Vaccination
- Prophylactic antipyretics or analgesics medication within 28 Days Post Vaccination
- Antipyretic or analgesic medication within 28 Days Post Vaccination

A summary table of concomitant medications and non-study vaccination that continued or newly received at or after the first vaccination through 28 days after the last vaccination will be provided by PT in descending frequency in the mRNA-1647 group with all dose level combined.

The summary tables will be based on the Safety Set.

Prior, concomitant and post medications and non-study vaccination will be presented in a listing.

Medications taken to treat or prevent pain or fever will be collected in the electronic diary (eDiary) within 7 days after vaccination and beyond 7 days after vaccination (if any solicited AR continues beyond 7 days). Summaries will be provided up to 28 days after vaccination based on the Solicited Safety Set by CMV serostatus (CMV-seropositive, CMV-seronegative, and overall) and vaccination group as defined in [Section 6.1](#) for each vaccination (first, second, third). Medications to treat or prevent pain or fever as collected in the eDiary will also be presented in a separate listing.

Concomitant Procedures will be presented in a listing.

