##### **6.5.1. Recording of Concomitant Medications and Non-study Vaccinations**

The following concomitant medication(s) and vaccine(s) must be recorded in the eCRF:

- All non-study vaccinations administered during the period starting  $\leq 28$  days before the first dose of study vaccine.
- COVID-19 vaccination (regardless of type of vaccine) will be recorded anytime from Day 1 through the End of the Study (Day 504)
- All concomitant medications and non-study vaccinations taken through 28 days after each vaccination. Antipyretics and analgesics taken prophylactically (ie, taken in the absence of any symptoms in anticipation of a vaccination reaction) will be recorded as such.
- Any concomitant medications relevant to or for the treatment of an SAE or a MAAE.

- Prophylactic medications (ie, medication administered in the absence of any symptom and in anticipation of a reaction to the vaccination) from Day 1 through 28 days after each dose. For example, an antipyretic or analgesic is considered to be prophylactic when it is given in the absence of fever and any other symptom, to prevent fever from occurring.
- Participant will be asked if they have taken any antipyretic or analgesic to treat or prevent fever or pain in the electronic diary (eDiary) within 7 days post vaccination, including day of vaccination. Reported antipyretic or analgesic medications should be recorded in the source document by the site staff during the post vaccination study visits or via other participant interactions (eg, phone calls).

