At each vaccination visit, participants will be instructed (Visit Day 1) or reminded (Visit Day 56 and Day 168) on thermometer usage to measure body temperature, ruler usage to measure injection site erythema and swelling/induration (hardness), and self-assessment for localized axillary swelling or tenderness ipsilateral to the vaccination arm. Participants will record body temperature, any solicited local (injection site) and systemic ARs, and whether any medications were taken to prevent or treat pain or fever starting on the day of each vaccination visit, at approximately 1 hour post vaccination under supervision of the clinical site staff to ensure successful entry of assessments. The site staff will perform any re-training as necessary. Thereafter, the participant will be instructed to complete the eDiary later that day, preferably in the evening and at the same time each day on the 6 subsequent days post vaccination. If any solicited ARs are ongoing at 7 days post vaccination, the participant will be prompted to capture the ongoing solicited ARs in the eDiary until it is no longer reported. Adverse reactions recorded in eDiaries beyond Day 7 should be reviewed either via phone call or at the following study visit.

Site personnel will review completed eDiary assessments during discussion with the participants on Day 8, Day 29, Day 56, Day 63, Day 84, Day 175, and Day 196, as applicable.

Additionally, delegated site staff will interview the participant to assess the occurrence of any unsolicited AEs, SAEs and medications taken. Unsolicited AEs will be captured from Day 1 through 28 days after each dose, and MAAEs from Day 1 to Day 336. SAEs will be captured from time of informed consent to the end of the study. The Investigator or designated site staff will transcribe the collected information into the eCRF.

The only source documents allowed for solicited systemic and local ARs (including body temperature measurements) will be the eDiary. The following additional rules apply to documentation of safety information collected using eDiary:

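### The eDiary summary of pain and fever medication runs to 28 days, but after Day 7 the eDiary collects it only while a solicited reaction is ongoing

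*SAP*

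**What the plan says.** SAP 6.2.4 has two sources for medication taken against pain or fever.

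- **eDiary.** Collection is described as "within 7 days after vaccination and beyond 7 days after vaccination (if any solicited AR continues beyond 7 days", so it becomes conditional after the first week. The next sentence sets the reporting: "Summaries will be provided up to 28 days after vaccination based on the Solicited Safety Set", split by serostatus and vaccination group for each vaccination. A separate listing of the eDiary entries is also planned.
- **Concomitant-medication data.** The list of tables on the Safety Set includes "Antipyretic or analgesic medication within 28 Days Post Vaccination", along with prophylactic use over the same period. Protocol 6.5.1 requires the eCRF to hold "All concomitant medications and non-study vaccinations taken through 28 days after each vaccination", with no condition on having a reaction.

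The protocol's account of the eDiary question is narrower than the SAP's. Protocol 6.5.1 says participants are asked about antipyretics and analgesics "in the electronic diary (eDiary) within 7 days post vaccination, including day of vaccination". Protocol 8.9.1.3 says that after the seventh day "the participant will be prompted to capture the ongoing solicited ARs in the eDiary until it is no longer reported"; it does not mention medication at that stage.

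The general rule for percentages is in SAP 6.1: "The denominator for all percentages will be the number of subjects in that vaccination group within the analysis set of interest", unless stated otherwise. SAP 6.2.4 states nothing otherwise for this summary.

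**The concern.** The reporting window is four times the window in which everyone is asked. A participant whose reactions end within the first week has no eDiary opportunity to report a tablet taken on Day 12, yet stays in the denominator of a summary that runs to Day 28. A participant with a lingering reaction does have that opportunity, for as long as the reaction lasts. The resulting percentage is neither 7-day use nor 28-day use, and how long each person is observed depends on reaction duration, which is itself a safety outcome.

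The clinical study report could then carry two 28-day summaries of analgesic and antipyretic use, one from the eDiary and one from the concomitant-medication data, that disagree because they were ascertained differently, with nothing to tell the reader why.

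**Working it through.** The plan gives no figure for medication use, or for reactions lasting beyond Day 7, in either arm. There is nothing to reproduce, so the check is textual first and then illustrative.

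**1. Windows set side by side.** Full collection covers the vaccination day and 6 subsequent days, so 7/28 = 25% of the reporting window. Collection is conditional for the other 21/28 = 75%. Membership of the per-vaccination Solicited Safety Sets (SAP 5.2) requires eDiary data from the vaccination day and the 6 days after it, so it does not guarantee any information on Days 8-28.

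**2. Direction of the error.** Let P7 be the proportion using medication in Days 1-7, u the proportion of the remainder who first use it in Days 8-28, and q the share of those first-time users who have an ongoing reaction when they do.

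- True 28-day use = P7 + (1 - P7)u
- Use visible to the eDiary = P7 + (1 - P7)uq
- Missed = (1 - P7)u(1 - q)

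The missed part is never negative, and it is above zero whenever P7 < 1, u > 0 and q < 1. No assumed rate is needed for that conclusion.

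**3. Possible size within a group.** Assume a constant, independent daily probability h of use and no collection after Day 7. Then 7-day use is 1 - (1 - h)^7 and 28-day use is 1 - (1 - h)^28.

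| h (assumed) | Captured in 7 days | True 28-day use | Share missed |
|---|---|---|---|
| 1% | 6.8% | 24.5% | 72% |
| 2% | 13.2% | 43.2% | 69% |
| 3% | 19.2% | 57.4% | 66.5% |

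**4. Possible effect on the vaccine-placebo difference.** Using the formulas in step 2, with u taken as equal in both arms and every input assumed:

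- P7 50% vs 15%, q 5% vs 1%, u = 5%: missed is 0.50 × 0.05 × 0.95 = 2.4 points in vaccine and 0.85 × 0.05 × 0.99 = 4.2 points in placebo. The difference is overstated by 1.8 points.
- Same P7 and q, u = 30%: missed is 14.3 and 25.2 points. The overstatement is 11.0 points.
- P7 30% in both arms, q 10% vs 2%, u from 5% to 30%: the overstatement is 0.70 × u × 0.08, or 0.3 to 1.7 points.
- P7 and q equal in both arms: zero.

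In the 11.0-point case, setting q to 1% in both arms still leaves 0.2525 - 0.50 × 0.30 × 0.99 = 0.104, or 10.4 points. Longer observation of vaccinees therefore accounts for about 0.6 point; the rest comes from the assumed gap in Day 1-7 use.

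**5. Precedent within the SAP.** SAP 6.3.2 faces the same conditional collection for the reactions themselves. It tabulates incidence over the 7-day period and puts reactions that continue into separate listings, with the extra days counted only in the duration summary. The medication summary departs from that practice without a stated reason.

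**The case against.** The best defence is that the 28-day question is already answered. The eCRF records concomitant medication for every participant through 28 days after each dose, and SAP 6.2.4 tabulates antipyretic and analgesic use from those data on the Safety Set. This stands, and it limits the point to a supplementary summary. Medication use is not an endpoint, and the study tests no hypothesis.

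It can also be said that the 28 days is only an outer limit on eDiary entries, since the condition on collection is stated in the sentence just before. The SAP speaks of summaries, not of one cumulative percentage, and the table shells are not available. That reading is possible, but nothing in the text separates Days 1-7 from later days, and the default denominator applies as written.

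A reader might go further and infer that the table is biased between vaccine and placebo, because the people not observed after Day 7 are mainly placebo recipients. The documents do not support this. Protocol 2.3 expects about 339 vaccine and 113 placebo participants. Even if no placebo recipient had a prolonged reaction, more than 339 - 113 = 226 vaccinees, two-thirds of them, would need one before placebo recipients formed the majority of those without. Protocol 2.3.2 describes most Phase 1 reactions as brief. A differential remains possible, but its size depends on rates that are not given, and under the assumptions tried it runs from nothing to 11 points.

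Finally, the repair hardly alters the displayed contrast. In the 11.0-point case the eDiary would show 50.75% vs 15.26%, a gap of 35.5 points; a 7-day summary would show 50% vs 15%, a gap of 35.0. That is fair. The gain is a figure that means what its label says.

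**Conclusion.** The mismatch is real and follows from the text alone: collection after Day 7 is conditional, the summary runs to Day 28, and the default denominator is the whole vaccination group in the Solicited Safety Set. Read as 28-day use, the percentage is under-ascertained, and observation time varies with reaction duration.

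Its size cannot be established from the documents. The shortfall of roughly two-thirds to 72% in the illustration rests on an assumed constant daily use of 1% to 3%, independence between days, no reaction-driven use and no collection after Day 7. A vaccine-placebo distortion should be described as possible, not as demonstrated.

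This is a minor point. It affects one supplementary descriptive summary of a variable that is not an endpoint, beside a 28-day table built on data recorded for everyone. It is worth correcting because the correction is nearly free and avoids two unexplained, conflicting 28-day figures.

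**What to change.** In SAP 6.2.4:

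- Limit the eDiary medication summary to the day of vaccination and the 6 subsequent days for each dose.
- Show eDiary use after Day 7 in the listing already planned or, if a table is wanted, separately with participants who have an ongoing solicited reaction as the denominator.
- Take 28-day antipyretic and analgesic use only from the concomitant-medication data, as the section already provides.
- Reconcile the SAP's statement of what the eDiary collects after Day 7 with the 7-day question in Protocol 6.5.1.

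The cost is a short wording change before the final database lock, with no new data. The one downside is that medication use tied to prolonged reactions leaves the main eDiary table; the separate display keeps it visible.
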